**Table 2 Treatment Arms, Dosing Frequencies and Patient Numbers**

Treatment Arms	Study Treatment	Dosing Frequency	N
1	Roxadustat	TIW	375
2	ESA	Dosing per SmPC	375

TIW = 3 times weekly; ESA = epoetin alfa or darbepoetin alfa; SmPC = Summary of Product Characteristics

During the treatment period, subjects will attend weekly study visits from day 1 to week 8, followed by every other week study visits from week 10 to 36. Following week 36, study visits will occur every 4 weeks until the End of Treatment (EOT).

Randomization and administration of the first dose of study treatment (roxadustat or ESA) is to occur on day 1 which should correspond to a day when their next dose of epoetin or darbepoetin alfa would have been administered.

On day 1 all study procedures and assessments will be completed prior to the first study treatment administration.

During the treatment period, the aim is to maintain the Hb levels between 10.0 g/dL and 12.0 g/dL. All subjects receiving roxadustat will initiate and continue roxadustat dosing at a dosing frequency of TIW throughout the entire period and dose adjustment is to follow prespecified dose adjustment rules [Table 4]. Intake should occur at approximately the same time of day and, if possible, dosing days should remain consistent throughout the study. For HD subjects it is recommended that roxadustat is administered any time after completion of dialysis if dosing is scheduled on a dialysis day to avoid potential bias on certain study assessments. Specific rules apply on the dialysis day(s) at which PK sampling is scheduled [Section 5.6].

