### EU (EMA)

Results from simulations of the EU primary efficacy endpoint in stable dialysis subjects suggest that dosing levels of ESA prior to randomization may play a role in Hb response. Therefore, the EU primary analysis of this study will be tested both in the overall population and in the subgroup of patients defined as subjects with an average prescribed weekly epoetin or darbepoetin dose within the last 4 weeks prior to randomization  $\leq 200$  IU/kg or  $\leq 1$   $\mu\text{g}/\text{kg}$  respectively, following a parametric chain procedure [Millen et al, 2011; Spiessens et al, 2010]. The information fraction will be calculated at the time of database hard lock; it is defined as the number of subjects in the subgroup with respect to the number of subjects in the total study population.

Assuming that the Per Protocol Set (PPS) analysis will consist of 80% of the randomized subjects, 750 randomized subjects will lead to approximately 600 subjects in the PPS. The overall 1-sided significance level (alpha) is fixed at 0.025 and the non-inferiority margin for the EU primary endpoint has been fixed to 0.75 g/dL. The overall alpha will be equally allocated to each of the 2 test populations. If we assume an information fraction of 0.80, this rule will lead to a significance level of 0.0174.

In this setting, 300 subjects for the roxadustat treatment group and 300 subjects for the ESA treatment group will provide 97% power to statistically demonstrate noninferiority of roxadustat versus ESA in the EU primary endpoint in both the total study population and the planned subgroup analysis assuming a difference (roxadustat minus ESA) of -0.25 g/dL in the Hb change from baseline and an SD of 1.5 g/dL. In the case that these assumptions do not hold across the overall population, the planned procedure can still allow for a successful conclusion for the subgroup.

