7.4.1.1 EU (EMA) Primary Endpoint

7.4.1.1.1 Primary Analysis of the EU (EMA) Primary Endpoint

The primary EU (EMA) efficacy endpoint will be analyzed using the PPS.

The change from baseline to the average Hb of weeks 28 to 36, without having received rescue therapy within 6 weeks prior to and during this 8-week period, will be computed from the Mixed Model of Repeated Measures method (MMRM), adjusting for stratification factors (covariates defined below), comparing roxadustat to ESA (pooled darbepoetin alfa and epoetin alfa). After fitting the data, a computation statement will be added to the model to calculate the average Hb values estimate during the period under consideration.

Difference of least square means (roxadustat minus ESA) and its 2-sided $100*(1-\alpha*2)\%$ confidence interval will be estimated for the change from baseline to the average of weeks 28 to 36. The significance level α is fixed by the parametric chain procedure explained below.

The primary analysis of the EU (EMA) primary efficacy endpoint will be tested both in the overall population and in the subset of patients defined as subjects with an average prescribed weekly epoetin or darbepoetin dose within the last four weeks prior to randomization ≤ 200 IU/kg or ≤ 1 μ g/kg respectively, following a parametric chain procedure.

The two null hypotheses to be tested are:

- H_{A0} : Hb change from baseline to the average of weeks 28 to 36 in the roxadustat arm \leq Hb change from baseline to the average of weeks 28 to 36 in the ESA arm minus 0.75 g/dL in the total study population
- H_{B0} : Hb change from baseline to the average of weeks 28 to 36 in the roxadustat arm \leq Hb change from baseline to the average of weeks 28 to 36 in the ESA arm minus 0.75 g/dL in the subset population

The alternative hypotheses H_{A1} and H_{B1} are defined as the negation of the null hypotheses H_{A0} and H_{B0} respectively. The information fraction (subjects in the subset population/total study population) will be calculated at the time of database hardlock.

The overall one-sided significance level (alpha) is fixed at 0.025. The overall alpha will be equally allocated to each of the two null hypotheses defined above. In case of an information fraction of 0.80, this rule will lead to a significance level of 0.0174.

The following table ([Table 12](#)) lists a selection of one-sided significance levels (alpha) to be considered should the IF varies from the protocol.

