The model will contain treatment arm, region, CV History, previous ESA treatment, visits and visit by treatment as categorical variables. It will also contain baseline Hb and baseline Hb by visit as continuous variable.

The unstructured covariance pattern model will be used. If the algorithm for unstructured covariance pattern does not converge, then heterogeneous Toeplitz structure will be used. If this later model does not converge either, then the (homogeneous) Toeplitz structure will be tried. Finally, if none of them converge, first order autoregressive (AR (1)) as a covariance structure will be used to achieve convergence.

A similar model as the general example below will be used:

$$c_{ikjn} = \text{intercept} + \beta_n M_{\text{baseline},ikjn} + \tau_i + \alpha_n + (\alpha\tau)_{in} + \gamma_k + \varepsilon_{ikjn}$$

where

- c_{ikjn} is each analysis visit change from baseline of subject j in treatment arm i , and stratum k at time n ,
- β_n is the slope of c_{ikjn} at visit n as a function of the baseline Hb,
- $M_{\text{baseline},ikjn}$ is the baseline measurement of subject j in treatment arm i and stratum k at time n ,
- τ_i , is the mean effect of treatment arm i ,
- α_n is the mean effect at time n ,
- $(\alpha\tau)_{in}$ is the interaction term between treatment arm i and time n ,
- γ_k is the mean effect of stratum k ,
- ε_{ikjn} is the residual at time n for subject j in treatment arm i and stratum k .

The SAS procedure will be similar to the following:

```
proc mixed;
  class subject_id treatment previous_ESA_treatment region cv_history
    visit;
  model change = treatment previous_ESA_treatment region cv_history
    baseline_Hb visit treatment*visit;
  repeated visit /subject = subject id type=un;
  lsmeans visit*treatment / cl alpha = 0.05;
  estimate 'Roxadustat v.s. ESA averaged at weeks 28-36'
    treatment 1 -1
    treatment*visit 0 0 0 0 .. 0.2 0.2 0.2 0.2 0.2 -0.2 -0.2 -0.2
    -0.2 / cl;
  where visit in ('Week1', 'Week2', ..., 'Week8', 'Week10', ..., 'Week36');
run;
```

One analysis Hb value for each visit will be used, as defined in analysis windows in Section [7.11.4](#) and [Table 32](#)

Subjects receiving rescue therapy treatment within 6 weeks prior to and during this 8-week period will be set to missing and imputed similarly in the model (see Section [7.11.1](#) for imputation details).

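### If the unstructured EU primary MMRM fails to converge, two of its three fallback structures could understate the standard error when Hb variance grows over time, because no robust errors are specified

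*SAP*

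**What the plan says.** SAP 7.4.1.1.1 analyses change in Hb from baseline to the weeks 28-36 average with an MMRM. Its covariance is unstructured first, with a chain of replacements: "If the algorithm for unstructured covariance pattern does not converge, then heterogeneous Toeplitz structure will be used". Homogeneous Toeplitz comes next, and the chain ends: "Finally, if none of them converge, first order autoregressive (AR (1)) as a covariance structure will be used to achieve convergence".

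The sample PROC MIXED code in that section models weeks 1 to 8 and weeks 10 to 36. Protocol 2.2.1.3 has weekly visits to week 8, "followed by every other week study visits from week 10 to 36". The code contains neither an EMPIRICAL nor a DDFM option, and neither document mentions robust errors. Model-based errors are therefore an inference, because the code is offered only as an approximate pattern.

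The lower confidence limit from this model decides EU success against -0.75 g/dL. Protocol 7.4.1.1 names only the unstructured matrix; the chain appears only in the SAP.

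**The concern.** Homogeneous Toeplitz and AR(1) estimate a single variance for all visits. Seventeen of the 22 modelled visits come before week 28. If early variances are smaller, the common estimate falls below the variance at the five visits that form the endpoint, and a model-based standard error carries that shortfall into the interval.

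Growing variance is plausible here. Subjects enter with three screening Hb values within 1.3 g/dL of each other (Protocol 3.2, criterion 6). Baseline is the mean of four values (SAP 6.1.1.1). One arm then changes drug, and roxadustat dose adjustments begin at week 4 (Protocol 5.1.2.1). Neither document gives a variance by visit, so this remains an assumption.

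At stake is the error rate of the EU non-inferiority test, which the SAP otherwise sets to four decimals in Table 12.

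**Working it through.** **Inputs from the plan**
- Overall level: "The overall one-sided significance level (alpha) is fixed at 0.025".
- First-step level: "In case of an information fraction of 0.80, this rule will lead to a significance level of 0.0174".
- Margin (Protocol 7.1): "the non-inferiority margin for the EU primary endpoint has been fixed to 0.75 g/dL".
- Size (Protocol 7.1): "300 subjects for the roxadustat treatment group and 300 subjects for the ESA treatment group".
- Planning values (Protocol 7.1): "assuming a difference (roxadustat minus ESA) of -0.25 g/dL in the Hb change from baseline and an SD of 1.5 g/dL".

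**1. The plan's own figures reproduce.** Two test statistics with correlation √0.80 and a joint rejection probability of 0.025 give 0.01737 each, that is 0.0174. The planning standard error is 1.5 × √(2/300) = 0.1225 g/dL and z(1 − 0.0174) = 2.111. Power is Φ((0.75 − 0.25)/0.1225 − 2.111) = Φ(1.97) = 97.6%, against the stated 97%. (This is for the overall population at 0.0174.)

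**2. Size of the model.** There are 8 weekly and 14 two-weekly visits, 22 in all.
- Unstructured: 22 × 23/2 = 253 covariance parameters.
- Heterogeneous Toeplitz: 22 + 21 = 43.
- Homogeneous Toeplitz: 22.
- AR(1): 2.

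**3. Method.** Take an assumed true covariance V over the 22 visits. Fit each fallback structure W by minimising log|W| + tr(W⁻¹V), the large-sample likelihood fit. With weights c = 1/5 on weeks 28, 30, 32, 34 and 36, the ratio of model-based to true standard error is r = √(c′Wc / c′Vc). The actual one-sided error at nominal 0.0174 is Φ(−2.111 × r). The ratio does not depend on the scale of V.

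**4. Three assumed covariances, complete data (t, u in weeks)**
- A: variance 1 throughout, correlation exp(−|t−u|/10). Only the unequal spacing is misfitted.
- B: 0.3² at each visit plus exp(−|t−u|/10) − exp(−(t+u)/10). The SD is √(0.09 + 1 − e^−0.2) = 0.52 at week 1 and 1.04 at week 36.
- C: 0.4² at each visit plus 0.4[exp(−|t−u|/8) − exp(−(t+u)/8)] + 0.6 g(t)g(u), with g(t) = min(t/20, 1). The SD is 0.50 at week 1 and 1.08 at week 36.

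| | Heterogeneous Toeplitz | Homogeneous Toeplitz | AR(1) |
|---|---|---|---|
| A: r (error) | 1.15 (0.008) | 1.02 (0.015) | 1.02 (0.015) |
| B: r (error) | 0.95 (0.022) | 0.89 (0.031) | 0.87 (0.034) |
| C: r (error) | 0.82 (0.041) | 0.79 (0.047) | 0.75 (0.056) |

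**5. Range over all the patterns tried.** With constant variance, every ratio lay between 0.96 and 1.15. With growing variance, homogeneous Toeplitz gave 0.78-0.91 and AR(1) 0.72-0.89. Heterogeneous Toeplitz gave 0.82-1.15. Where it was tried, 20% monotone dropout hardly changed the ratios. As a guide, r = 0.90 gives Φ(−1.900) = 0.029 and r = 0.80 gives Φ(−1.689) = 0.046.

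**6. Effect on the decision.** At the planning values the half-width is 2.111 × 0.1225 = 0.259 and the lower limit is −0.25 − 0.259 = −0.51 g/dL. At r = 0.80 these become 0.207 and −0.46. Both limits clear −0.75. The verdict would differ only for an estimated difference between −0.75 + 0.207 = −0.543 and −0.75 + 0.259 = −0.491.

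**7. With sandwich errors** r is 1 in large samples under any of these structures, and the error returns to 0.0174 (0.025 at the second step of the chain).

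**The case against.** The strongest objection is that the trigger is not shown. Counting 253 parameters does not establish that the unstructured fit will fail with about 600 subjects, and AR(1) is reached only after three failures. In a check with 22 visits, 25% dropout and 5% intermittent missingness, an unstructured fit converged in 180 of 180 runs at 600 subjects and 180 of 180 at 450. That check used Fisher-scoring maximum likelihood with arm-by-visit means, not PROC MIXED with all covariates. The low-dose subset adds little risk, since SAP 7.4.1.1.1 says the high-dose group was too small to be useful as a covariate. This stands: the risk is conditional, and nothing in the documents makes it probable.

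A second objection is that sensitivity analyses S5 to S7 (SAP Table 13) estimate the same endpoint without these structures, so an oddly narrow primary interval would be visible beside them. That stands in part. SAP 7.4.1.1.2 limits them to confidence intervals without tests and to the total population, and the residual plots do not check the covariance structure.

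A reader might infer that unequal spacing is what narrows the interval. Pattern A shows otherwise: spacing alone leaves it about right or somewhat wide. A reader might also extend the point to every MMRM that refers to this section. The LDL model has five scheduled post-baseline visits to week 28 (5 × 6/2 = 15 parameters) and the SF-36 models three (6 parameters), so failure there is remote. IV iron use is analysed by ANCOVA.

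**Conclusion.** The point holds in a limited form. If the unstructured fit fails and the analysis reaches homogeneous Toeplitz or AR(1), the weeks 28-36 standard error could be understated by roughly 10-20%, taking a one-sided 0.0174 to about 0.03-0.05. The steepest assumed patterns went further under AR(1), to a ratio of 0.72 and an error of 0.063. Heterogeneous Toeplitz may be conservative or anti-conservative.

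This rests on three assumptions: variance that grows after the switch, model-based errors as the sample code implies, and a failed unstructured fit. The documents establish neither the first nor the last. They therefore do not support saying that the EU interval will be too narrow or that the EU conclusion is unsafe. The inflated error matters when the true difference is near −0.75 g/dL; at the planning difference of −0.25 the conclusion is the same either way. Exposure is mainly in the many-visit models: Hb, and mean arterial pressure (SAP 7.4.2.6), which has a 1 mmHg margin.

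It is worth correcting because a prespecified fallback should keep the error rate of the analysis it replaces.

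**What to change.** Keep the unstructured matrix first. Add one sentence to SAP 7.4.1.1.1: any fallback covariance structure will be used with empirical (sandwich) standard errors, through the EMPIRICAL option in PROC MIXED. The MAP analysis, which refers to that section, would then inherit the rule.

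The cost is one sentence and one option. Small-sample corrections of the Kenward-Roger type are not available with sandwich errors, which is minor at about 600 subjects. Sandwich errors repair the interval's width but not any bias in the point estimate when data are missing and the covariance is misspecified.

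Optionally, insert a named heterogeneous structure such as ANTE(1), which allows visit-specific variances and adjacent correlations, before the homogeneous steps. Keep a simple final step so that the plan still ends in a model that will converge.

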7.4.1.1.2 Secondary Analyses (sensitivity) of the EU (EMA) Primary Endpoint

The following analyses will be done as sensitivity analyses of the EU (EMA) primary endpoint:

- The primary analysis will be repeated on the FAS and All Randomized;
- The primary endpoint will be analyzed similarly as for the primary analysis, but regardless of rescue therapy, on the PPS and FAS.
- The primary endpoint will be analyzed using an ANCOVA and Multiple Imputation (MI) of data, and including the same covariates, on the PPS.
- The primary endpoint will be analyzed using different Pattern Mixture Models (PMM) with different assumptions for missing patterns, including the same covariates, on the PPS.

All sensitivity analyses will be done on the total population.

The analysis using MMRM will be similar to the one provided in Section 7.4.1.1.1

For all sensitivity analyses, no hypothesis testing will be done, only confidence intervals presented and graphically represented in a forest plot.

Table 13 summarizes all sensitivity analyses to be performed with the EU (EMA) primary endpoint.

Table 13 Primary and Sensitivity Analyses for the EU (EMA) Primary Endpoint

Code	Set	Population	Endpoint	Model	Covariates*
Primary	PPS	Total	Change to the Average Hb in weeks 28-36, without rescue therapy	MMRM	Region, History of CV, Previous ESA treatment, Visits and Visit by Treatment, BL Hb by visit, BL Hb
S1	FAS	Total	Change to the Average Hb in weeks 28-36, without rescue therapy	MMRM	Region, History of CV, Previous ESA treatment, Visits and Visit by Treatment, BL Hb by visit, BL Hb
S2	All Randomized	Total	Change to the Average Hb in weeks 28-36, without rescue therapy	MMRM	Region, History of CV, Previous ESA treatment, Visits and Visit by Treatment, BL Hb by visit, BL Hb
S3	PPS	Total	Change to the Average Hb in weeks 28-36, regardless of rescue therapy	MMRM	Region, History of CV, Previous ESA treatment, Visits and Visit by Treatment, BL Hb by visit, BL Hb
S4	FAS	Total	Change to the Average Hb in weeks 28-36, regardless of rescue therapy	MMRM	Region, History of CV, Previous ESA treatment, Visits and Visit by Treatment, BL Hb by visit, BL Hb
S5	PPS	Total	Change to the Average Hb in weeks 28-36, without rescue therapy	ANCOVA with MI	Region, History of CV, Previous ESA treatment, BL Hb
S6	PPS	Total	Change to the Average Hb in weeks 28-36, without rescue therapy	PMM (Last mean carried forward)	Region, History of CV, Previous ESA treatment, BL Hb
S7	PPS	Total	Change to the Average Hb in weeks 28-36, without rescue therapy	PMM – Last Mean Carried Forward for Roxadustat and Randomized arm MAR for ESAs	Region, History of CV, Previous ESA treatment, BL Hb

ANCOVA with MI:

The sensitivity analysis using ANCOVA with MI will be similar to the primary analysis of the US endpoint, provided in Section [7.4.1.2.1](#)

Pattern Mixture Models (PMM)

Pattern Mixture models will be used as an alternative to impute missing values, using different assumptions for missing patterns.

PMMs provide a general and flexible framework for sensitivity analyses that allows formulating assumptions regarding missing data in a transparent and clinically interpretable manner. This is expected to address the possibility of the data being missing not at random. All factors mentioned in the primary analysis will be included in the PMM (refer to Section [7.4.1.1.1](#)).

The following aspects of data missingness, may affect the estimates.

- Timing and extent of missingness
- Assumed underlying mechanism for data missingness

A. Timing and Extent of Missing Data

To assess the potential effect of data missingness on the estimate of treatment effect, subjects will be classified as full data or missing data cases. Patterns of missingness will be based on non-missing hemoglobin before the end of the evaluation period.

- Full data cases are defined as subjects with non-missing hemoglobin for all scheduled weeks of the Treatment period.
- Missing data cases are defined as subjects with a missing hemoglobin on at least one scheduled Week of the treatment period. The missing data cases are further grouped into intermittent missing and monotone missing cases.
 - Intermittent missing hemoglobin cases are defined as subjects with a missing hemoglobin for at least one scheduled week of but not on consecutive scheduled weeks up to end of the evaluation period.
 - Monotone missing hemoglobin cases are defined as subjects who have consecutive scheduled Weeks with missing hemoglobin up to the end of evaluation period. A subject who is a Monotone missing case could have intermittent missing hemoglobin prior to the ending Week.

Subjects will be grouped as follows:

- Full data cases
- Intermittent missing data cases
- Monotone missing data cases

Should the incidence of monotone missing data cases and intermittent missing data cases be relatively small, then those cases will be combined so that the groups are full data cases and missing data cases. The summary of missing patterns in the first 36 scheduled visits will be presented in a table/graph.

B. Assumptions on Missing Data Mechanism

In addition to the extent of data missingness, the mechanism under which missing data occur may affect the estimate of the parameter of interest.

The potential impact of missing efficacy endpoints on the estimates of treatment effects will be assessed using alternative statistical models with different underlying assumptions on the missing data mechanism for Missing Not AT Random (MNAR) (Little and Rubin, 1987).

C. PMM - Last Mean Carried Forward

A pattern-mixture model using a last mean carried forward multiple imputation method (Carpenter et al, 2013) will be used as another sensitivity analysis to explore the robustness of the MMRM and ANCOVA with MI results for the primary efficacy variable. Using this method, missing data after ending week will be imputed based on the last non-missing mean from its own treatment group.

D. PMM –Mixed (Last Mean Carried Forward for Roxadustat and Randomized Arm MAR for Active Comparator)

This method is a combination of PMM-Last Mean Carried forward for Roxadustat and PMM-Randomized Arm Missing At Random (MAR) for ESA group. The imputation data will be generated based on last mean carried forward method described above for the Roxadustat treatment group, while for the ESA group, the imputation data will be generated using the Randomized Arm MAR group described below.

The Randomized Arm MAR is similar to PMM-Last Mean Carried Forward except that the joint distribution of the patient's observed and missing data is multivariate normal with mean and covariance matrix from their randomized treatment group.

The ANCOVA model will then be performed for each combined imputed complete data set. Similarly, the Rubin's method will be then used to combine the estimates and the differences between the least square mean differences between the two treatment groups from each of the ANCOVA analyses.

Model checking:

Residual plots will be produced showing the following:

- Model residuals in the y-axis and model predictions in the x-axis,
- Model residuals in the y-axis and baseline Hb in the x-axis.

Different dot styles will be used for the two treatment arms. Solid black symbols will be used for roxadustat and non-solid red symbols will be used for ESA.

Residual plots will be done for the ANCOVA analysis. In addition, an empirical cumulative distribution function of the residuals will be plotted for the same ANCOVA analysis.

If a relevant baseline variable is identified for which a clinically important imbalance exists at baseline between treatment groups, additional sensitivity analyses of the primary endpoint

may be performed using an ANCOVA model adjusting for this baseline variable. This will allow us to assess the impact of these imbalances on the treatment comparisons.

